## 8.0 STUDY PLAN

### 8.1 Study Procedures

The following sections describe the study procedures and data to be collected. For each procedure, subjects are to be assessed by the same investigator or site personnel whenever possible. The Schedule of Study Procedures is located in [Appendix A](#).

#### 8.1.1 Informed Consent Procedure

The requirements of the informed consent are described in [Section 15.2](#).

Informed consent must be obtained prior to the subject entering into the study, and before any protocol-directed procedures are performed.

A unique subject Screening number will be assigned to each subject at the time that the informed consent is obtained; this Screening number will be used until the subject has been randomized into the study, at which time the Subject number will be primary method of identification on study records.

##### 8.1.1.1 *Pharmacogenomic Informed Consent Procedure*

Pharmacogenomics informed consent is a component of the overall study informed consent. The requirements are described in [Section 15.2](#).

The pharmacogenomic sample collection is optional.

#### 8.1.2 Demographics, Medical History, and Medication History Procedure

Demographic information to be obtained will include date of birth, sex, Hispanic ethnicity, race as described by the subject, height, weight, caffeine consumption, reproductive status (including last menstrual period) and smoking status of the subject at Screening.

Medical history to be obtained will include determining whether the subject has any significant conditions or diseases relevant to the disease under study that stopped at or prior to signing of informed consent. Ongoing conditions are considered concurrent medical conditions (see [Section 9.1.7](#)).

Medication history information to be obtained includes any medication relevant to eligibility criteria stopped at or within 45 days (for subjects with schizophrenia) prior to signing of informed consent.

#### 8.1.3 Physical Examination Procedure

A physical examination will consist of the following body systems: (1) eyes; (2) ears, nose, throat; (3) cardiovascular system; (4) respiratory system; (5) gastrointestinal system; (6) dermatologic system; (7) extremities; (8) musculoskeletal system; (9) nervous system; (10) lymph nodes; and (11) other.

Any abnormal change from the initial Screening physical examination must be assessed by the investigator as not clinically significant (NCS) or clinically significant (CS) and recorded in the source document and eCRF.

Any CS change, as determined by the investigator, from the baseline physical examination will be recorded as an AE or pretreatment event in source documentation and on the Pretreatment Event/AE eCRF.

#### **8.1.4 Weight, Height, and BMI**

A subject should have weight and height measured while wearing indoor clothing and with shoes off. The BMI is calculated using metric units with the formula provided below:

The standard for collecting height is centimeters without decimal places and for weight it is kilograms (kg) with 1 decimal place. BMI should be derived as:

$$\text{Metric: } \text{BMI} = \text{weight (kg)}/\text{height (m)}^2$$

Note that although height is measured in centimeters, the BMI formula uses meters for height; meters can be determined by dividing centimeters by 100. Thus, for example, if height=176 cm (1.76 m) and weight=79.2 kg, then  $\text{BMI}=79.2/1.76^2=25.56818 \text{ kg/m}^2$ .

Results for BMI will be expressed with 1 decimal place and rounding is allowed. The above value should be captured as  $25.6 \text{ kg/m}^2$  in the database.

#### **8.1.5 Vital Sign Procedure**

When vital signs are scheduled at the same time as blood draws, the blood draw will take priority and vital signs will be obtained within 0.5 hour before or after the scheduled blood draw.

Vital signs consisting of body temperature (oral), respiration rate, blood pressure and pulse will be measured in a seated resting state ( $\geq 10$  minutes).

#### **8.1.6 Documentation of Concomitant Medications**

Concomitant medication is any drug given in addition to the study medication. These may be prescribed by a physician or obtained by the subject over the counter. Concomitant medication is not provided by Cerevance. At each study visit, subjects will be asked whether they have taken any medication other than the study medication (used from signing of informed consent through the end of the study), and all medication including vitamin supplements, OTC medications, and oral herbal preparations, must be recorded in the eCRF. Documentation will include generic medication name, dose, unit, frequency, route of administration, start and end dates, and reason for use.

#### **8.1.7 Documentation of Concurrent Medical Conditions**

Concurrent medical conditions are those significant ongoing conditions or diseases that are present at signing of informed consent. This includes clinically significant laboratory, ECG, or physical examination abnormalities noted at the Screening examination. The condition (i.e., diagnosis) should be described.

#### **8.1.8 Procedures for Clinical Laboratory Samples**

All samples will be collected in accordance with acceptable laboratory procedures and as stipulated in the Schedule of Study Procedures ([Appendix A](#)). Abnormal Screening labs may be

repeated once at the discretion of the investigator for assessment of eligibility. Subjects who still do not meet eligibility criteria may be re-screened at investigator's discretion.

Table 9.a lists the tests that will be obtained for each laboratory specimen

**Table 9.a Clinical Laboratory Tests**

Hematology	Serum Chemistry	Urinalysis
RBC	ALT	pH
WBC with differential (%) and absolute)	Albumin	Specific gravity
Hemoglobin	Alkaline phosphatase	Protein
Hematocrit	AST	Glucose
Platelets	Total bilirubin	Blood
Prothrombin time /INR	Direct bilirubin	Nitrite
	Total protein	Microscopic Analysis (only if positive dipstick results):
	Creatinine	RBC/high power field
	Blood urea nitrogen	WBC/high power field
	Creatine kinase	Epithelial cells, casts etc
	GGT	
	Potassium	
	Sodium	
	Glucose	
	Chloride	
	Bicarbonate	
	Calcium	
Diagnostic Screening:		
Serum	Urine	Saliva (d)
Serum hCG (a)	Drug screen including amphetamines, barbiturates, benzodiazepines, cannabinoids, cocaine, opiates, alcohol, and cotinine (c)	Alcohol
At Screening Only:		cotinine
Hepatitis panel, including HBsAg and anti-HCV		
FSH (b)		

FSH=follicle-stimulating hormone, GGT=γ-glutamyl transferase, RBC=red blood cells, WBC=white blood cells.

(a) Serum hCG pregnancy test will be done at Screening.

(b) FSH level will be obtained for female subjects at Screening if they are postmenopausal (i.e., last regular menstrual cycle >2 years) and not surgically sterile. The result must be >40 IU/L to obviate the need for contraception.

(c) To be performed at Screening.

(d) Alcohol and cotinine saliva samples may be collected, if needed.

The local laboratory will perform laboratory tests for hematology, serum chemistries, and urinalysis. The results of laboratory tests will be returned to the investigator, who is responsible for reviewing and filing these results.

If subjects experience ALT or AST >3 ×ULN, follow-up laboratory tests (at a minimum, serum alkaline phosphatase, ALT, AST, total bilirubin, GGT, and INR) should be performed within a maximum of 7 days and preferably within 48 to 72 hours after the abnormality was noted.

(Please refer to [Section 7.5](#) for discontinuation criteria, and [Section 10.2.3](#) for the appropriate guidance on Reporting of Abnormal Liver Function Tests in relation to ALT or AST >3 ×ULN in conjunction with total bilirubin >2 ×ULN.)

If the ALT or AST remains elevated  $>3 \times \text{ULN}$  on these 2 consecutive occasions, the investigator must contact the Medical Monitor for consideration of additional testing, close monitoring, possible discontinuation of study medication, discussion of the relevant subject details and possible alternative etiologies. The abnormality should be recorded as an AE (please refer to [Section 10.2.3 Reporting of Abnormal Liver Function Tests](#) for reporting requirements).

All laboratory safety data will be transferred electronically to Cerevance or designee in the format requested by Cerevance. If the laboratory is unable to electronically transfer data, the study site coordinator or designee is responsible for transcribing laboratory results into the eCRF. The investigator will maintain a copy of the laboratory accreditation and the reference ranges for the laboratory used.

Laboratory reports must be signed and dated by the PI or sub-investigator indicating that the report has been reviewed and any abnormalities have been assessed for clinical significance.

All CS laboratory abnormalities must be recorded as a PTE/AE in the subject's source documents and on the appropriate eCRF. A CS laboratory abnormality that has been verified by retesting will be followed until the abnormality returns to an acceptable level or a satisfactory explanation has been obtained.

### 8.1.9 Contraception and Pregnancy Avoidance Procedure

During the study and for 12 weeks after last dose of study medication, nonsterilized males and female subjects of childbearing potential who are sexually active must agree to use two effective methods of contraception.

From signing of informed consent, throughout the duration of the study, and for 12 weeks after last dose of study medication, nonsterilized\*\* male subjects who are sexually active with a female partner of childbearing potential\* must use barrier contraception (e.g., condom with spermicidal cream or jelly). In addition, they must be advised not to donate sperm during this period.

From signing of informed consent, throughout the duration of the study, and for 12 weeks after last dose of study medication, female subjects of childbearing potential\* who are sexually active with a nonsterilized male partner\*\* must use adequate contraception. In addition they must be advised not to donate ova during this period.

\*Females NOT of childbearing potential are defined as those who have been surgically sterilized (hysterectomy, bilateral oophorectomy or tubal ligation) or who are postmenopausal (e.g., defined as at least 2 years since last regular menses with an FSH $>40$  IU/L or at least 5 years since last regular menses, confirmed before any study medication is implemented).

\*\*Sterilized males should be at least 1 year postvasectomy and have confirmed that they have obtained documentation of the absence of sperm in the ejaculate.

The following are acceptable forms of contraception:

**Barrier methods (each time the subject has intercourse):    Intrauterine devices (IUDs):**

- Male condom PLUS spermicide.
- Cap (plus spermicidal cream or jelly).
- Diaphragm (plus spermicidal cream or jelly).
- Copper T PLUS condom or spermicide.

**Hormonal Contraception (stable regimen)**

- Birth control pills or patch.
- Injected hormonal contraceptive (such as Depo-Provera).
- Vaginal hormonal ring (such as NuvaRing).

Subjects will be provided with information on acceptable methods of contraception as part of the subject informed consent process and will be asked to sign a consent form stating that they understand the requirements for avoidance of pregnancy, donation of ova, and sperm donation during the course of the study.

During the course of the study, regular serum human chorionic gonadotropin (hCG) pregnancy tests will be performed only for women of childbearing potential, and subjects will receive guidance with respect to the avoidance of pregnancy. In addition to a negative serum hCG pregnancy test at Screening, subjects also must have a negative urine hCG pregnancy test prior to receiving any dose of study medication. Male subjects must be advised not to donate sperm from signing of informed consent to 12 weeks after the last dose of study medication.

**8.1.10 Pregnancy**

If any subject is found to be pregnant during the study she should be withdrawn and any sponsor-supplied drug should be immediately discontinued. In addition, any pregnancies in the partner of a male subject during the study or for 12 weeks after the last dose should also be recorded following authorization from the subject's partner.

If the pregnancy occurs during administration of active study medication, e.g., after Visit 1 or within 12 weeks of the last dose of active study medication, the pregnancy should be reported immediately, using a pregnancy notification form, to the contact listed in [Section 1.0](#).

Should the pregnancy occur during or after administration of blinded drug, the investigator must inform the subject of their right to receive treatment information. If the subject chooses to receive unblinded treatment information, the individual blind should be broken by the investigator. Subjects who have only received placebo need not be followed.

If the female subject and/or female partner of a male subject agrees to the primary care physician being informed, the investigator should notify the primary care physician that the subject/female partner of the subject was participating in a clinical study at the time she became pregnant and provide details of treatment the subject received (blinded or unblinded, as applicable).

All reported pregnancies will be followed up to final outcome, using the pregnancy form. The outcome, including any premature termination, must be reported to the sponsor. An evaluation after the birth of the child will also be conducted.

### 8.1.11 ECG Procedure

A standard 12-lead ECG will be recorded in a supine position resting for at least 10 minutes at Screening to assess eligibility. The ECGs will be recorded in triplicate at approximately 5 minute intervals. The investigator (or a qualified physician at the investigational site) will interpret the ECG using 1 of the following categories: within normal limits, abnormal but NCS, or abnormal and CS. A copy of the ECG trace should be kept with the subject's notes.

ECGs will be read automatically and also, the investigator or sub-investigator or a suitably qualified delegate will manually interpret the ECG using 1 of the following categories: within normal limits, abnormal NCS, or abnormal and CS. All 12-lead ECGs will be stored for manual measurement of intervals, if necessary.

Twelve-lead ECGs will be recorded using an ECG machine that automatically calculates the heart rate and measures PR interval, RR interval, QRS interval, QT interval, and QTcF and QTcB (Fridericia's and Bazett's correction) intervals.

One copy of the 12-lead ECG with the physician's signature and date of assessment will be filed with the source documents and captured in the appropriate eCRF. All ECGs will be recorded at the time points detailed in the Schedule of Study Procedures ([Appendix A](#)).

### 8.1.12 Pharmacogenomic Sample Collection

Every subject must sign informed consent/be consented in order to participate in the study, but consent to participate in the pharmacogenomic sample collection (genetic substudy) is optional.

Deoxyribonucleic acid (DNA) and ribonucleic acid (RNA) form the basis for the genes that make the body produce proteins such as enzymes, drug transporters or drug targets, and may be evaluated for the genetic contribution how the drug is broken down, or how the drug affects the body. This is called a "pharmacogenomics research study." Specific purposes of this study include:

- Identifying genetic reasons why certain people respond differently to CVN058.
- Finding out more information about how CVN058 works.
- Generating information needed for research, development, and regulatory approval of tests to predict response to CVN058.
- Identifying variations in genes related to the biological target of CVN058.

This information may be used, for example, to develop a better understanding of the safety and efficacy of CVN058 and other study medications, and for improving the efficiency, design and study methods of future research studies.

The DNA samples will be used to evaluate common variations in genes which encode drug metabolizing enzymes and transporters. This could be helpful in understanding why there are differences in CVN058 kinetics between subjects. Also, since pharmacogenomics is an evolving

science, many genes and their functions are not yet fully understood. Future data may suggest a role of some of these genes in drug response, which may lead to additional hypothesis-generating exploratory research and diagnostic development on stored samples.

Whole blood will be collected and stored for possible DNA or RNA isolation and analysis.

DNA sample collection:

One 6 mL whole blood sample will be collected before study drug dosing on Day 1 of Period 1 only from each subject in the study, into plastic potassium ethylenediamine tetraacetic acid (K2EDTA) spray-coated tubes, and stored under frozen conditions.

RNA sample collection:

Two whole blood samples (2.5 mL per sample) will be collected from each subject into a PAXgene tube on Day 1 of each period at pre dose and post EEG for RNA pharmacogenomic analysis.

If isolation of DNA from the first sample was not successful or possible, a second aliquot of blood may be taken, if feasible.

Each pharmacogenomic sample for a study subject should be identifiable on the requisition form with the 7-digit subject ID. Detailed instructions for the handling, shipping, and storage of pharmacogenomic samples will be provided in the lab manual.

The samples will be stored for no longer than 15 years after completion of the CVN058 study and/or until the drug development of CVN058 is no longer actively pursued by Cerevance or its collaborators. No samples will be stored for longer than permitted by the applicable law and samples will be destroyed upon notification from Cerevance.

### 8.1.13 Pharmacokinetic Sample Collection

#### 8.1.13.1 Collection of Blood for Pharmacokinetic Sampling

Blood samples (one 6-mL sample per scheduled time) will be collected for analysis of CVN058, and its metabolite if appropriate; plasma will be collected into chilled vacutainers containing K2EDTA according to the schedule in [Appendix A](#). Instructions for sample processing and shipment will be provided in the lab manual.

Serial blood samples for determination of CVN058, and its metabolite if appropriate, in plasma will be collected according to [Table 9.b](#).

**Table 9.b Collection of Blood Samples for CVN058 Pharmacokinetic Analysis**

Sample Type	Dosing Day	Time Postdose (hours)
Plasma	1	Predose (within 15 minutes prior to dosing), 1 hour post dose (pre-EEG), and 5 hours post dose (post-EEG)

The PK samples will be collected before any other assessments are performed, if scheduled at the same time point. The actual time of sample collection will be recorded on the source document and eCRF.

Placebo samples will not be analyzed by the bioanalytical laboratory except 1 sample per subject receiving placebo around the expected time at which CVN058 Cmax is expected to occur to ensure from a safety perspective that no subjects have inadvertently received active treatment.

#### 8.1.13.2 Bioanalytical Methods

Plasma concentrations of CVN058 will be measured by high-performance liquid chromatography with tandem mass spectrometry. If appropriate, plasma samples analyzed for CVN058 also may be analyzed for the CVN058 metabolite.

### 8.1.14 Pharmacokinetic Parameters

The PK parameters of CVN058, and its metabolite (if appropriate), will be derived using non-compartmental analysis methods. The PK parameters will be determined from the concentration-time data for all evaluable subjects. Actual sampling times, rather than scheduled sampling times, will be used in all computations involving sampling times. The following PK parameters will be determined from concentrations of CVN058, and its metabolite if appropriate, in plasma. Other parameters may be calculated as appropriate.

Symbol/Term	Definition
Plasma	
AUC t	Area under the plasma concentration-time curve from time 0 to time of the last quantifiable concentration.
C max	Maximum observed plasma concentration.
t max	Time to reach C max .

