#### 4.3 Clinical

Two human clinical studies of CVN058 have been completed (ENV8058\_101 and TAK-058-1002).

CVN058 was well tolerated up to a dose of 150 mg administered orally as a single dose in aqueous solution (Study ENV8058\_101). There were no deaths or other serious adverse events (SAEs) reported in this study and no subject discontinued study due to a treatment-emergent adverse event (TEAE). There were no clinically significant (CS) laboratory abnormalities, electrocardiogram (ECG) changes or changes in vital signs in the completed single dose study.

The mean  $C_{max}$  and area under the plasma concentration–time curve (AUC) values of CVN058 increased less than proportionally with increasing CVN058 dose across the dose range of 5 to 150 mg, but mean  $C_{max}$  and AUC values increase in an approximately dose proportional manner across the 5 to 45 mg dose range. The rate of appearance of CVN058 in plasma was rapid with median time to  $C_{max}$  ( $t_{max}$ ) values of 1 to 1.25 hours across the dose range of 5 to 150 mg. The mean terminal elimination half-life ( $t_{1/2z}$ ) values of CVN058 ranged from approximately 2.8 to 10.5 hours across the cohorts; the lower doses (5 to 30 mg) had lower mean  $t_{1/2z}$  values compared to the higher doses (45 to 150 mg). There were no trends with mean apparent clearance (CL/F) values of CVN058 with increasing dose from 5 to 45 mg, but faster apparent clearance was observed at the 75 and 150 mg doses, possibly due to decreased bioavailability (BA) at higher doses. The mean apparent volume of distribution ( $V_z/F$ ) increased as dose increased. Excretion of unchanged CVN058 in the urine was  $\leq 2.3\%$  of the administered CVN058 dose over the dose range evaluated.

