**Table 9.b      Collection of Blood Samples for CVN058 Pharmacokinetic Analysis**

Sample Type	Dosing Day	Time Postdose (hours)
Plasma	1	Predose (within 15 minutes prior to dosing), 1 hour post dose (pre-EEG), and 5 hours post dose (post-EEG)

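### With samples only at 1 h and 5 h after dosing, tmax cannot be estimated; Cmax is in effect C1h, and AUCt is a partial area to 5 h

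*Protocol*

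**What the plan says.** The schedule is in Table 9.b, identical in Versions 2.0 and 3.0: "Predose (within 15 minutes prior to dosing), 1 hour post dose (pre-EEG), and 5 hours post dose (post-EEG"). Version 1.0 had the last sample at 4 h. Version 2.0 section 8.1.13.1 specifies "one 6-mL sample per scheduled time".

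Version 2.0 section 8.1.14 introduces AUCt, Cmax and tmax with "The following PK parameters will be determined from concentrations of CVN058, and its metabolite if appropriate, in plasma", states that the parameters "will be derived using non-compartmental analysis methods", and adds: "Actual sampling times, rather than scheduled sampling times, will be used in all computations involving sampling times". Cmax is defined there as "Maximum observed plasma concentration", and AUCt as the area up to the last quantifiable concentration. All three are exploratory endpoints (Version 2.0 section 4.2.3, Version 3.0 section 5.2.3). Version 2.0 sections 12.1.3 and 12.1.4 plan descriptive summaries and graphical exposure-response, and name no exposure metric for the plots.

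On the earlier single-dose study, section 4.3 of Version 3.0 (3.3 in Version 2.0) reports median tmax "values of 1 to 1.25 hours across the dose range of 5 to 150 mg". It reports mean terminal half-lives that "ranged from approximately 2.8 to 10.5 hours across the cohorts", lower at 5-30 mg than at 45-150 mg.

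**The concern.** Non-compartmental Cmax and tmax are read off the sampled points, and AUCt joins those points by trapezoids. With two post-dose points, 4 h apart and on either side of a long EEG session, nothing is observed in between. A parameter can then be named as an endpoint and yet carry almost no information about the drug.

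At stake is how the PK summary will be read. A median tmax of about 1 h would look like agreement with the earlier 1 to 1.25 h, although the schedule almost forces that answer. An AUCt row shown for 15 mg and 150 mg could be taken for total exposure, when the part beyond 5 h is missing and is not the same fraction at each dose. The MMN comparison with placebo does not depend on any of this.

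**Working it through.** **The plan's own figure.** Three samples per period × 3 periods = 9 samples; 9 × 6 mL = 54 mL; 25 + 5 + 3 + 54 + 6 + 30 = 123 mL. This matches Table 9.c (Version 2.0) and confirms two post-dose samples per period.

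**tmax.** Version 2.0 Table 14.a allows ±5 minutes at 1 h and ±15 minutes at 5 h. Recorded tmax must therefore lie within about 0.92-1.08 h or 4.75-5.25 h if the windows are kept. It is about 1 h whenever C1h exceeds C5h, and about 5 h otherwise.

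**Cmax and AUCt.** Inputs from the protocol: tmax 1 and 1.25 h; half-life 2.8 and 10.5 h. Assumed: a one-compartment oral model, scaled to unit dose over volume.

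- ke = ln 2 / half-life = 0.2476 or 0.0660 per h
- ka solved from tmax = ln(ka/ke)/(ka − ke)
- C(t) = ka/(ka − ke) × [exp(−ke·t) − exp(−ka·t)]
- Linear trapezoid, 0 to 5 h = 0.5·C1 + 2·(C1 + C5)
- Total area = 1/ke

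Worked case, half-life 2.8 h and tmax 1.25 h (ka = 1.862):

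- C1 = 0.7212, C5 = 0.3344, true peak 0.7339. Observed/true peak = 0.7212/0.7339 = 0.983.
- Trapezoid = 0.3606 + 2 × 1.0556 = 2.472. True 0-5 h area 2.688, so the ratio is 0.919.
- Share of total area = 2.688 × 0.2476 = 0.67.

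| Half-life | True tmax | Recorded tmax | Observed/true Cmax | Trapezoid/true AUC(0-5h), linear | Same, linear-log | AUC(0-5h)/total |
|---|---|---|---|---|---|---|
| 2.8 h | 1 h | 1 h | 1.00 | 0.945 | 0.90 | 0.68 |
| 2.8 h | 1.25 h | 1 h | 0.98 | 0.92 | 0.88 | 0.67 |
| 10.5 h | 1 h | 1 h | 1.00 | 0.93 | 0.93 | 0.27 |
| 10.5 h | 1.25 h | 1 h | 0.99 | 0.93 | 0.93 | 0.27 |

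**Later tmax (assumption).** The protocol lets subjects eat before each visit but gives no food-effect figure.

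- True tmax 2 h: recorded tmax still 1 h; Cmax ratio 0.84-0.89; linear AUC ratio 0.84-0.90.
- True tmax 3 h: recorded tmax jumps to 5 h; Cmax ratio 0.86-0.93; linear AUC ratio 0.83-0.87.

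True values of 1 h and 2 h thus give the same record, and 3 h is recorded as 5 h.

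**Spread between subjects (assumption).** With lognormal tmax, median 1 or 1.25 h and CV 30% or 50%:

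- only 36-62% of subjects have a true tmax within 0.25 h of 1 h, yet all but 0.2-12% are recorded at 1 h;
- the mean Cmax ratio is 0.94-0.99 (5th percentile 0.80-0.95);
- the mean linear AUC ratio is 0.90-0.93.

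**The case against.** The strongest reply is that Cmax and AUCt are defined operationally, as an observed maximum and an area to the last quantifiable value, so both can be computed exactly as defined. The 1 h sample sits near the documented median peak. This stands. A reader might infer that none of the three parameters can be estimated, but the documents do not support that for Cmax or AUCt. Shortfalls of 16-17% require a true tmax of 2-3 h, which no passage reports. Even the direction of the AUC error depends on the model: biexponential variants gave ratios of 0.96-1.04, although their peaks fell at 0.61-0.87 h, earlier than the documented medians.

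A reader might also infer that exposure-response will use the wrong axis. No axis metric is named, and concentrations at each sampling time are summarised anyway. The two samples also bracket the recording. By Appendix A (Version 2.0) it runs from about 1.5 h to 1.5 + 3 = 4.5 h; counting the 30-minute set-up in section 8.1.16 after the 1.5 h mark, it ends at 1.5 + 0.5 + 3 = 5 h. Predicting the concentration at the MMN time from a phase 1 model would be an optional refinement of an exploratory graph.

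Finally, a reader might set 67% against 27% as the shares of total exposure captured at 15 mg and 150 mg. The protocol does not assign 2.8 h or 10.5 h to those doses. Only the direction follows: with longer half-lives at 45-150 mg, a 0-5 h area captures a smaller share at the higher dose.

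None of this rescues tmax. The protocol itself fixes the schedule, the method and the endpoint, so this is not a detail left to the SAP.

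**Conclusion.** The point holds for tmax without qualification: it is a named endpoint that the sampling cannot estimate. For the other two it is a matter of labelling and interpretation. Cmax is in effect C1h, within about 2% of the true peak if tmax is 1-1.25 h. AUCt is a partial area over 0-5 h, about 5-8% low by linear trapezoids (about 7-12% by linear-log) at that tmax, and it is not total exposure. It captures a smaller share of total exposure at 150 mg than at 15 mg, by an amount the documents do not allow one to derive.

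The percentages rest on the one-compartment shape and on the earlier study's medians applying here. The tmax conclusion needs neither.

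Severity is minor, because the endpoints are exploratory and descriptive. Version 3.0 keeps the same samples and endpoints, but its text breaks off before the PK parameter section, and Versions 4.0 and 5.0 are not shown. Whether the point survives in the final protocol is therefore unverified.

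**What to change.** In the exploratory endpoints (Version 2.0 section 4.2.3, Version 3.0 section 5.2.3), the PK parameter section (8.1.14 and 9.1.14 respectively) and the study summary:

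- Drop tmax.
- Report observed C1h and C5h at actual sampling times.
- Label the area AUC(0-5h) where the 5 h value is quantifiable, and state that it is not total exposure and is not to be read as such across doses.
- In the pharmacodynamic analysis section, name the observed C1h and C5h as the exposure measures for the exposure-response plots.

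Align the summary statistics in the PK analysis section with the new names, and check the wording against Versions 4.0 and 5.0. The cost is a wording change and the loss of a nominal tmax row; no sample, visit or blood volume is added.
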